Participants should be seen for all visits/assessments as outlined in the assessment schedule (Table 8-1) or as close to the designated day/time as possible. Missed or rescheduled visits should not lead to automatic discontinuation. Participants who prematurely discontinue the study for any reason should be scheduled for a visit as soon as possible, at which time all of the assessments listed for the final visit will be performed. At this final visit, the adverse event and concomitant medications should be recorded on the CRF. Unscheduled on-site visits are possible e.g. to repeat sampling in case of lost or unusable samples, in case of suspected safety issues. Additional telephone visits shall be scheduled in case of booster/refresher SARS-CoV-2 vaccinations to document type and date of the booster vaccination. Additionally, 1 month (+/- 1 week) after a potential booster vaccination a booster visit will be scheduled that includes all assessments performed in the regular study visit 3 including the drawing of blood samples. If this booster visit falls within +/- 1 week of the regular visit 3 or later than the telephone contact in month 12, it will not be performed.

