8.1 Documentation of IMPs

Both MS DMTs and SARS-CoV-2 vaccinations are considered as IMPs in this study. As part of drug accountability the following documentation of IMP treatment is required to allow a valid analysis of immune responses to vaccinations in combination with MS treatment.

Documentation of MS DMTs

- At screening
 - Documentation of the current prescription and lot number (Ch-B) of the currently applied MS DMT and number of remaining doses in the package. This information may also be obtained via telephone.
- Investigational epoch (Month 1-12 after vaccination)
 - Documentation of all re-newed MS-DMT prescriptions including lot numbers (Ch-B) of the medication packages. For this purpose, patients should bring any new and empty MS DMT packages (including empty blisters) to the next possible study visit for documentation purposes. Ch-B numbers may also be obtained via telephone contacts.

Should patients fail to bring new or empty MS DMT packages and blisters to the study center even after documented reminders it is also allowed to calculate the compliance from the interval of prescriptions. The compliance as judged by the treating physician shall be documented in the eCRF.

Documentation of SARS-CoV-2 vaccinations

- Vaccination at external site
 - A scan/copy of the "Impfpass" document

- Documentation timepoint of vaccination (date and hour)
- Documentation which external site performed vaccination
- **Vaccination within clinic but outside study site**
 - A scan/copy of the “Impfpass” document
 - Documentation timepoint of vaccination (date and hour)
 - Documentation of department and responsible person for vaccination
 - Confirmation that vaccination was performed according to clinical routine
 - Confirmation that temperature log cannot be obtained
- **Vaccination at study site**
 - **Preparation of syringes directly after delivery to study site**
 - Documentation DSL authorization
 - Documentation timepoint syringe preparation (to make sure 6h at room temperature is not exceeded)
 - Documentation temperature log of refrigerator (if used for storage)
 - A scan/copy of the “Impfpass” document
 - Documentation timepoint of vaccination (date and hour)
 - **Preparation of syringes NOT directly after delivery to study site**
 - Documentation DSL authorization
 - Documentation temperature log of refrigerator
 - Documentation timepoint syringe preparation (to make sure 6h at room temperature is not exceeded)

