8.3.2 Information to be collected on screening failures

Participants who sign an informed consent form and subsequently found to be ineligible will be considered a screen failure. The reason for screen failure should be entered on the applicable Case Report Form. The demographic information, informed consent, and Inclusion/Exclusion pages must also be completed for screen failure participants. No other data will be entered into the clinical database for participants who are screen failures, unless the participant experienced a serious adverse event during the screening phase (see SAE section for reporting details).

Table 8-1 Assessment schedule

Period	Screening	Vaccination [#]		Investigational					COVID-19 follow-up call	
Visit	Screen	Vaccination 1 [#]	Vaccination 2 [#]	1	2	3	booster vaccination ^Q	booster visit ^Q	Call (end of study)	
Day/Week/Month	Day -30 to -3	Day 1*	Week 3/4*	Week +1 (day 8 +/- 2)	Month +1 (day 28-35)	Month +6 (week 25-27)	any time	Month +1 (+/- 1 week) after booster vaccination	Month +12 (week 50-54)	
Obtain informed consent	X									
Inclusion/exclusion criteria	X									
Demography, Relevant medical and MS history	X									
Physical exam including vital signs, height weight	F			S	S	F		F		
SARS-CoV-2 PCR test**	X									
Urine pregnancy test***	X						X		X	
Blood sampling	X			X	X	X			X	
MS relapse	X****	X	X	X	X	X	X	X		
Status MS- and concomitant medication	X	X	X	X	X	X	X	X		X
Documentation SARS-CoV-2 vaccination		X	X				X			
Telephone contact		X	X				X		X	
AE/SAE	X	X	X	X	X	X	X	X	X	

X = assessment to be recorded in the clinical database or received electronically from a vendor

F = full physical exam, S = short medical exam

[#] modRNA vaccination using the same type of compound in both vaccinations independent of study site at designated vaccination centers as part of clinical routine and depending on federal regulations; vaccination will be performed according to respective EU SmPC. Booster/refresher vaccinations are allowed in this study, if suggested by local regulations and performed as part of clinical routine. ^QIf booster/refresher vaccinations are performed an additional telephone contact is required matching documentation parameters shown above for vaccination 1 and 2.

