^QFurthermore, an additional study visit will be performed one month (+/- 1 week) after the booster vaccination matching all assessments of investigational visit 3. If this unscheduled visit falls within +/- 1 week of the regular visit 3 or later than the telephone contact in month 12, it will not be performed. * Number of required vaccinations and interval depends on the SmPC of the respective modRNA vaccination. ** Patients need to be sent into quarantine immediately in case of positive test results. Patients in this study are only allowed to continue the study and receive SARS-CoV-2 vaccination after they received a negative PCR test result. *** Required minimum of sensitivity of the pregnancy test is HCG 25 mIU/mL. **** MS relapses within the last two years should be recorded.

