## 2.7 Analysis of secondary efficacy objective(s)

### 2.7.1 Secondary endpoints

The secondary endpoints are analyzed descriptively within each cohort. The efficacy analysis set is used for all analyses of the secondary parameters.

The semiquantitative SARS-CoV-2 serum functional antibody titer (percent inhibition) is summarized by arithmetic mean, standard deviation, minimum, median and maximum by visit. A boxplot graph will be presented.

The SARS-CoV-2 serum functional antibody titer is summarized by geometric mean, geometric coefficient of variation (CV) and 95% confidence intervals for the (geometric) mean. The Visits Screening, Visit 1/Week 1, Visit 2 /Month 1 and Visit3 /Month 6 are displayed separately in this summary table and a boxplot graph with logarithmic y-axis (log base 10).

The same summary table and boxplot will be provided for the following secondary parameters:

- a) Qualitative and quantitative result of IFNg towards SARS-CoV-2 and towards coronaviridae
- b) Qualitative and quantitative result of IL-2 towards SARS-CoV-2 and towards coronaviridae
- c) Combined response in qualitative INFg or IL-s towards SARS-CoV-2 and towards coronaviridae, i. e. reactive to INFg or IL-2 or to both.
- d) Cell viability, CD3 lymphocytes, CD4 and CD8 cells, percentage of CD4+ and CD8+ cell in peripheral blood mononuclear cells

The percent inhibition values for INFg at screening will be displayed for the subset of patients who are reactive at Week 1 versus non-reactive. The same analysis is provided for IL-2.

All other laboratory data (e. g. number of basal/background spots, spots, quality, comments, mutations) are listed only.

The MS activity is measured by relapses. The crude annual relapse rate until end of study and underlying sums (of relapses and patient-years) will be presented.

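### SAP 2.7.1 does not define the person-time for the relapse rate, and no relapse item is scheduled at the Month-12 call

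*SAP*

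**What the plan says.** SAP 2.7.1 uses relapses as its measure of MS activity: "The crude annual relapse rate until end of study and underlying sums (of relapses and patient-years) will be presented". The SAP gives no start date, stop date or source of relapses for this rate. SAP 2.7.3, whose heading covers missing values, censoring and discontinuations, says only that missing values are not replaced. For adverse events, by contrast, SAP 5.2 sets a start, an end and a fallback when the Month-12 call is missing.

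Protocol Table 8-1 heads the Month-12 column (week 50-54) "Call (end of study". The Amendment 2 note on section 8.1 agrees, and section 8.1 itself is headed "Investigational epoch (Month 1-12 after vaccination". Protocol section 3 points the other way: it describes the call as asking about COVID-19 occurring once the study has ended.

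Table 8-1 also has rows for MS relapse, for AE/SAE and for "Status MS- and concomitant medication". Its footnotes add that after a booster "an additional telephone contact is required matching documentation parameters shown above for vaccination 1 and 2", and that "an additional study visit will be performed one month (+/- 1 week) after the booster vaccination matching all assessments of investigational visit 3". At screening the relapse item is a history: "MS relapses within the last two years should be recorded".

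**The concern.** A crude rate is meaningful only if numerator and denominator cover the same time. If patient-years run to the call while relapses are asked about only up to Visit 3, the denominator contains about half a year per patient in which no relapse question was scheduled, and the absolute rate comes out too low in every cohort.

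Boosters add an uneven element. A booster contact or visit after Visit 3 extends relapse assessment, but only in boosted patients. Cohorts with different booster uptake or timing could then differ for reasons unrelated to disease activity.

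The rate is descriptive, but it bears on a question that the protocol raises itself. Section 4.1 says that a return of disease activity has to be considered when siponimod is interrupted, and interruption is what separates Cohort 2 from Cohort 1.

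**Working it through.** **1. Which contacts carry the relapse item.** Table 8-1 has nine contacts: screening, Vaccinations 1 and 2, Visits 1 to 3, booster vaccination, booster visit and the call. The MS relapse row has eight marks; the AE/SAE and medication rows have nine each. Some columns of the table are shifted in the extracted text, so I did not rely on alignment. The footnotes tie the booster contact to Vaccinations 1 and 2 and the booster visit to Visit 3, all of which carry the item. Screening (1) + vaccinations (2) + visits (3) + booster contact (1) + booster visit (1) = 8. No mark is left for the call.

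**2. The plan's own duration.** Protocol section 3 gives 56-60 weeks per participant. The components are in the Amendment 1 summary: 1 + 3 + 52 = 56 and 4 + 4 + 52 = 60. The figure reproduces.

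**3. Time without scheduled relapse assessment, no later booster contact.** Nominal gap from Visit 3 to the call: 52 - 26 = 26 weeks (50 - 27 = 23 to 54 - 25 = 29 across the windows). As a share of follow-up from screening: 26/60 = 43% to 26/56 = 46%. Using the Table 8-1 screening window of 3-30 days (0.43-4.29 weeks) instead:
- shortest lead-in: 1 - (0.43 + 3 + 26)/(0.43 + 3 + 52) = 1 - 29.4/55.4 = 47%
- longest lead-in: 1 - (4.29 + 4 + 26)/(4.29 + 4 + 52) = 1 - 34.3/60.3 = 43%
- window extremes: 1 - 28.4/57.4 = about 50% and 1 - 35.3/58.3 = about 40%

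The start date is also undefined. Counted from the second dose, the nominal share would be 26/52 = 50%.

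**4. Effect on the rate.** Under a constant relapse rate, with person-time to the call and no relapse captured after Visit 3, the reported rate equals the true rate times (assessed weeks / total weeks). The shares in step 3 are therefore the worst-case shortfalls.

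**5. How the shortfall shrinks.** Take a middle case of 6 weeks from screening to second dose: 32/58 = 0.552, shortfall 44.8%. If a fraction q of later relapses is captured through other items (an assumption; the documents give no figure), the shortfall is 44.8% × (1 - q):

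| q | 0 | 25% | 50% | 75% | 100% |
|---|---|---|---|---|---|
| shortfall | 45% | 34% | 22% | 11% | 0% |

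For one boosted patient, a last relapse assessment at week 34 gives 1 - 40/58 = 31%, at week 39 1 - 45/58 = 22%, and at week 52 0%. SAP 2.5.4 says that several boosters were given before Visit 3. Where the booster visit also falls by then, it adds no coverage.

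**6. Patient-years, middle case, 52.18 weeks per year.** Cohort of 20: 20 × 58/52.18 = 22.2 to the call and 20 × 32/52.18 = 12.3 to Visit 3, a gap of 10.0. For 60 patients: 66.7 and 36.8, a gap of 29.9.

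**The case against.** The strongest reply is that the plan does not clearly run the denominator to Month 12. Protocol section 3 can be read as placing the end of the study before the call. SAP 1.1 puts the primary analysis at six months and treats Month 12 as a follow-up analysis, which SAP 2.8 describes only as amending the adverse event analyses. If end of study meant Visit 3, the shortfall would be about zero. This stands as a real conflict in the documents. Table 8-1, Protocol 8.1 and the Amendment 2 note make the call the better-supported reading, but either reading needs a written rule.

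Second, later relapses need not be lost. AE/SAE and MS medication are recorded at the call, and Protocol 10.1.1 continues AE monitoring for at least 30 days beyond it. This also stands, in part: AEs are sought by non-directive questioning, and neither document says that a relapse reported this way enters the relapse count.

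A reader might go further and infer three things that the documents do not support:
- That the rate will be nearly halved. That requires the Month-12 reading, no booster coverage and no other capture, all together.
- That the comparison of cohorts is distorted by a known amount or in a known direction. No document gives booster uptake by cohort.
- That relapses during the siponimod break go unasked. The planned break is about 2-3 months around vaccination, and relapse items run from screening to week 25-27. A later booster brings its own contact, and "1 month (+/- 1 week) after a potential booster vaccination a booster visit will be scheduled" unless it falls close to Visit 3 or after the call.

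Finally, the SAP will show both sums, so a reader can see the denominator, though not how much of it was assessed. Relapses reported as AEs would also appear in the AE tables.

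**Conclusion.** The point holds as a minor one. The SAP leaves the person-time of its relapse rate undefined. On the best-supported reading of end of study, it counts about 26 weeks per unboosted patient with no scheduled relapse assessment. The descriptive rate can then be too low by up to about 43-47%, assuming person-time from screening, nominal visit weeks, a constant relapse rate, no later booster contact and no capture through AE or medication items. Relaxing these last two assumptions, or reading end of study as Visit 3, brings the shortfall down, to 0% at the limit. Artificial differences between cohorts are possible through boosters, but their size and direction cannot be fixed from the documents. The primary endpoint and the endpoints in Protocol Table 2-1 are unaffected.

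**What to change.** State the rule in SAP 2.7.1 or 2.7.3:
- **Start:** a defined date, for example informed consent, with the two-year relapse history excluded.
- **End:** for both relapses and patient-years, the last contact at which relapse was actually assessed. That is Visit 3, a later booster contact or booster visit, or the final visit for those who leave before Visit 3.
- **Second rate:** if relapses reported as AEs up to the call are also counted, show them in a separate, labelled rate with person-time to the call.

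This is a wording change that uses dates already recorded. The SAP history dates its latest version after final data review, so the added rule should be reported as a dated clarification.

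The cost is precision: about 12 instead of 22 patient-years per cohort of 20. As an illustration, 3 relapses would give 3/12.27 = 0.24 per year (exact 95% Poisson limits 0.05-0.71) instead of 3/22.23 = 0.13 (0.03-0.39). The wider interval reflects the time in which relapses were actually asked about.

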- Participants in cohort 1: vaccination will be administered according to EU SmPC under continued siponimod treatment. In case of a booster vaccination, patients in this cohort may also undergo a treatment break which is also covered by the EU SmPC.
- Participants in cohort 2: vaccination will be administered according to EU SmPC after start of the siponimod treatment break.
- Participants in cohort 3: vaccination will be administered according to EU SmPC during continued treatment with first-line MS DMTs or no current treatment.

If suggested by local regulations, patients will be allowed to receive additional SARS-CoV-2 vaccinations (booster or refresher) during the study according to the physician's discretion and as part of the clinical routine. This booster may be any type of SARS-CoV-2 vaccine, depending on local regulations. According to SmPC, siponimod patients in Cohort 1 and Cohort 2 may introduce a treatment break for the purpose of the booster vaccination e.g. in case there was no measurable immune response during the initial vaccination cycle. The decision for such a treatment break is at the discretion of the treating physician and patient.

3. Investigational period

[figure not shown]
Blood samples for SARS-CoV-2 functional antibody titers and T-cells for primary and secondary endpoints will be drawn from all patients 1 week (day 6 - 10), 1 month (day 28 - 35)

and 6 months (week 25 - 27) after completion of vaccination. In case of booster vaccinations an additional blood sample will be collected one month (+/- 1 week after the booster vaccination).

12 months (week 50 – 54) after completion of the vaccination a COVID-19 follow-up call is scheduled to inquire about a possible confirmed COVID-19 disease after the end of the study.

In total, the study duration for each participant is 56-60 weeks, depending on the length of the screening period.

Figure 3-1 Study design

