It is unlikely that there will be a direct benefit to the patient as a result of the participation in this study other than receiving the information whether measurable SARS-CoV-2 antibody and T-cell levels are reached after the vaccination. This information can then be used to decide whether an additional booster vaccination might be necessary in MS patients with/without concomitant immunosuppressing/immunomodulating therapy. Furthermore, the results of the study will contribute to a better understanding of immune responses to modRNA vaccines in siponimod treated SPMS patients. Findings can inform physicians and patients if risk factor management may need to be reviewed and potentially give additional guidance for vaccination with the novel class of modRNA vaccines in MS patients.

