## **2.8 Safety analyses**

All safety analyses are presented for the Safety Set (SAF). Descriptive statistics are presented within study treatment groups (cohorts 1-3).

It should be mentioned that the follow-up analysis amends all analyses of adverse events. The CSR is planned to be finalized after this follow-up analysis.

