## **4 Change to protocol specified analyses**

The definition for the Efficacy analysis Set was adapted to avoid that non-missing secondary endpoints would be excluded from the efficacy analysis set. For the rate of seroconversion (primary parameter) the patients with missing data are already excluded from the denominator.

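### The crude annual relapse rate runs to end of study, but relapse is not scheduled for assessment in roughly the last six months before the Month-12 call

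*SAP*

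**What the plan says.** The last paragraph of SAP 2.7.1 measures MS activity by relapses: "The crude annual relapse rate until end of study and underlying sums (of relapses and patient-years) will be presented". It does not say when patient-years start, what end of study means for this rate, or where relapses are taken from. SAP 2.7.3, whose heading covers missing values, censoring and discontinuations, says only that missing values are not replaced.

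The protocol places the end of study in two ways:

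- Table 8-1 labels the Month +12 column "Call (end of study". Section 10.1.1 treats the COVID-19 follow-up call as the last study visit.
- Section 3, describing the same call, says that "a COVID-19 follow-up call is scheduled to inquire about a possible confirmed COVID-19 disease after the end of the study". On that wording the study has ended before the call.

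The MS relapse row of Table 8-1 is marked at screening, both vaccination contacts, Visits 1 to 3, the booster contact and the booster visit. As extracted, it has no mark for the call. At screening the row also looks back: "MS relapses within the last two years should be recorded".

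**The concern.** A crude rate is events divided by time at risk, and both must cover the same period. Here the denominator appears to run to the Month-12 call, while the scheduled source of events stops at Visit 3 for any patient without a later booster contact or visit. Time in which nobody was due to ask about relapse would count as relapse-free, and the rate would come out too low.

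The start is open as well. The relapse row holds two years of history from before screening, and the SAP does not say that this is left out.

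Return of disease activity is the risk that the protocol names for pausing siponimod (sections 1.1 and 4.1). This is the only annualised measure of MS activity in the SAP, so an understated rate could give false reassurance to a reader weighing a treatment break.

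**Working it through.** **Where the study ends.** Protocol section 3 gives 56 to 60 weeks per participant. The split appears only in the Amendment 1 summary: 1 to 4 weeks from screening to the first dose, 3 to 4 weeks between doses, and 52 weeks to the call.

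- 1 + 3 + 52 = 56 and 4 + 4 + 52 = 60, which reproduces the stated range.
- Ending at Visit 3 (nominal week 26) would give 1 + 3 + 26 = 30 to 4 + 4 + 26 = 34 weeks.

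The stated duration therefore includes the time to the call.

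**Inputs for the rate** (Table 8-1): screening 3 to 30 days before the first dose; second dose 3 or 4 weeks later; Visit 3 at weeks 25 to 27 and the call at weeks 50 to 54 after the second dose. The clock is assumed to start at screening, where consent is obtained. One year is 365.25/7 = 52.18 weeks.

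**Time covered by scheduled relapse assessment**

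- Shortest: 3/7 + 3 + 25 = 28.4 weeks
- Longest: 30/7 + 4 + 27 = 35.3 weeks

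**Time counted to the call**

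- Shortest: 3/7 + 3 + 50 = 53.4 weeks
- Longest: 30/7 + 4 + 54 = 62.3 weeks

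**Shortfall.** With a constant relapse rate and no relapse captured after Visit 3, shortfall = 1 − (weeks to Visit 3)/(weeks to call).

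- Early windows: 1 − 28.4/53.4 = 46.8%
- Late windows: 1 − 35.3/62.3 = 43.3%
- Early Visit 3 with late call (gap 54 − 25 = 29 weeks): 1 − 28.4/57.4 = 50.5%
- Late Visit 3 with early call (gap 50 − 27 = 23 weeks): 1 − 35.3/58.3 = 39.5%
- Clock started at the second dose, paired windows: 1 − 25/50 = 1 − 27/54 = 50%

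The nominal durations agree: 1 − 30/56 = 46.4% and 1 − 34/60 = 43.3%.

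**Illustration** (assumed: 22 patients, 3 relapses by Visit 3, none captured later)

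| Patient-years end at | Patient-years | Rate per year |
|---|---|---|
| Visit 3 | 22 × 28.4/52.18 = 12.0 to 22 × 35.3/52.18 = 14.9 | 3/12.0 = 0.25 to 3/14.9 = 0.20 |
| Month-12 call | 22 × 53.4/52.18 = 22.5 to 22 × 62.3/52.18 = 26.3 | 3/22.5 = 0.13 to 3/26.3 = 0.11 |

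**The case against.** The strongest reply is that the bias needs two premises the SAP does not state: that patient-years run to the call, and that relapses come only from scheduled relapse assessments.

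- **End point.** Section 3 of the protocol supports a Visit 3 reading. So does the SAP's timing: section 1.1 sets the primary analysis at six months, and section 2.8 says that "the follow-up analysis amends all analyses of adverse events", without mentioning relapse. This stands as a real ambiguity. The table label, section 10.1.1 and the stated duration still favour Month 12.
- **Late capture.** Table 8-1 records adverse events at the call and, on its likely reading, MS-medication status. Unscheduled visits are possible (protocol section 8). Some late relapses would surface this way, and those reported as adverse events would appear by cohort in the safety tables. This also stands. However, adverse events are sought by non-directive questioning (section 10.1.1), and the SAP does not say that relapses found this way enter the rate.
- **The table itself.** Column alignment was damaged in extraction; the blood-sampling row, read literally, puts a sample at a telephone call. The relapse row has eight consecutive marks and the adverse-event row has nine, so no relapse mark at the call is the likelier reading, but it should be checked against the original table.
- **Consequence.** With 3 events the exact 95% Poisson interval is about 0.6 to 8.8 events, wider than the shift. The relapse and patient-year sums are also shown, so a reader can see the time base. Both are fair, but neither removes a mismatch that is easy to avoid.

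Two stronger readings are tempting. A reader might infer that the bias differs between cohorts, because late boosters add relapse assessments and the protocol says of the measured response: "This information can then be used to decide whether an additional booster vaccination might be necessary". The documents give no booster timing after Visit 3. SAP 2.5.4 mentions only boosters before it, and those do not extend assessed time. A reader might also object to the patient set, since "The efficacy analysis set is used for all analyses of the secondary parameters". The effect is probably about zero. The exclusions in SAP 5.4 largely overlap the screening-failure definition, and SAP 4 says the set "was adapted to avoid that non-missing secondary endpoints would be excluded from the efficacy analysis set".

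**Conclusion.** The concern holds in a limited form. On the reading the documents mostly favour, the denominator includes about 23 to 29 weeks per patient with no scheduled relapse assessment, unless a booster contact or visit falls in that time.

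The resulting shortfall of about 43% to 47% (40% to 51% with mixed windows from screening) is an upper case and should not be read as the expected error. It assumes a constant relapse rate, patient-years to the call, and no relapse captured after Visit 3. Capture through adverse events or MS-medication status would reduce it by an amount the documents do not allow one to estimate. Reading end of study as Visit 3 makes it 0%.

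Severity is minor. The rate is descriptive, no test or decision depends on it, and relapse rate is not among the endpoints in protocol Table 2-1 or SAP 1.2, so no departure from the protocol is claimed.

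**What to change.** Replace the sentence on the relapse rate in SAP 2.7.1 with wording such as:

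> The crude annual relapse rate and the underlying sums of relapses and patient-years are presented by cohort. Only relapses starting on or after informed consent count. Patient-years run from informed consent to the patient's last visit or contact at which MS relapse was assessed (Visit 3, or a later booster contact, booster visit or unscheduled visit). Relapses known only from adverse events at the Month-12 call are listed separately.

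This costs one reworded sentence, one end-date derivation and one short listing. It needs no new data.

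The price is roughly half the patient-years: for 22 patients, about 12 to 15 instead of 23 to 26. Late relapses known only as adverse events stay outside the rate. An unscheduled visit prompted by a relapse lengthens follow-up only for a patient who relapsed, so the number of such visits should be shown beside the rate.
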